Health service use will be collected from patient-report via telephone or in-person at 6, 12, and 18 months after completion of treatment, as well as from medical records. Patients will be supplied with a calendar and asked to note office visits, hospitalizations, emergency department visits, prescriptions, tests, and other health resource use. We will also provide participants with a tip sheet for tracking providers visited, care received, tests done, and prescriptions obtained. The tip sheet template has been adapted from the Medical Expenditure Panel Survey, courtesy of the Agency for Healthcare Research & Quality (see study supplemental documents) (Cohen, et al., 1996). At each data collection point, patients will use these resources to report what health services they have received during the past 6 months.

We will also request and abstract the medical record of each participant for the 18-month study period. The abstraction will focus specifically on surveillance and preventive care. We will also collect all health service use during the study period (outpatient visits, tests, imaging studies, hospitalizations, emergency department visits, medication list). These data will allow us to explore receipt of other preventive and screening services that may be age-based and/or not required on an annual basis (e.g., cholesterol screening, cervical cancer screening), as well as overall health service use (see supplemental study documents for Health Services Use document) .

Patient-reported outcomes will be collected at baseline, 6, 12, and 18 months. The default mechanism for these contacts will be via a REDcap form, with a link sent to the participants via email (see supplemental study documents for Pro Data Collection form). Where this is not possible, the research staff will collect data on the telephone, by mail or in-person.

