- Assessment of Survivor Concerns (ASC): The Assessment of Survivor Concerns is a 5-item questionnaire that assesses two subscales: cancer worry and general health worry. Each item is rated on a 4-point scale from 1=not at all to 4=very much. Subscale scores and an overall score are calculated by summing the relevant items. The ASC was developed by Gotay & Pagano and used in a previous study of survivorship care planning (Gotay, C. C., & Pagano, I. S., 2007; Hershman, D. L., et al., 2013).
- Follow-up Care Use among Survivors (FOCUS)-Information Needs Module: The FOCUS information needs questionnaire asks about the need for information regarding 12 topics (Kent, E. E., et al., 2012) Response options are “no,” “yes,” and “not sure.” It was developed by the National Cancer Institute based on previously published information needs questionnaires (Beckjord, E. B., et al., 2008; Mallinger, et al., 2005; Nelson, et al., 2004). The FOCUS study included an evaluation of the impact of survivorship care plans on information needs.

The PROs will be collecting using REDCap (see supplemental study documents). Patients who do not complete the PROs electronically prior to the health-service use follow-up phone calls will have the opportunity to complete the PROs over the phone, by mail, or in-person.

c. Statistical plan including sample size justification and interim data analysis.

No interim analyses are planned.

SAMPLE SIZE: We will recruit 250 participants through JHMI and 125 participants at PRMC oncology program practices (see Table 2). This weighting of recruitment reflects the difference in the number of patients seen at each site, and the fact that we will be studying three separate clinical settings within a large academic center versus a rural based community cancer program. Based on 2011/2012 cancer registry data from each site, our desired sample size is feasible based on approximately 680 breast, 676 colorectal, and 1310 prostate cancer cases newly seen per year at JHMI, and approximately 187 breast, 96 colorectal, and 206 prostate cancer cases newly seen per year at PRMC. To ensure balanced randomization between the three arms, we will stratify by site (JHMI or PRMC) and by cancer type (breast, prostate, or colorectal).

Table 2: Recruitment by Site

Sites	JHMI N=250			PRMC Oncology Program Practices N=125		
Tumor Groups	Breast (n=100)	Colorectal (n=50)	Prostate (n=100)	Breast (n=50)	Colorectal (n=25)	Prostate (n=50)
Arm A	34	17	33	17	8	17

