Although it is not the primary outcome of this study, the PROs are important secondary outcomes in survivorship care planning. Therefore, we have also calculated the power our sample size has to detect meaningful differences in the PROs across the study arms. PROs will be compared among study arms using linear regression and ANOVA. PRO values at follow-up visits will be modeled as a function of study arm while adjusting for the baseline value and other patient characteristics. Because patients are randomized, there should be no difference in PRO scores or other characteristics between patients at baseline. Given that we will be using a range of different PRO questionnaires and the evidence that differences of one-half a standard deviation are meaningful (Norman et al, Medical Care 2003), these power calculations were conducted to estimate the power to detect differences in standard deviations. For each power calculation, outcomes were simulated from a random normal distribution using the mean (SD) specified in the table for each study arm. Values were compared between arms using ANOVA, and power was calculated as the proportion of simulations that yielded a $p < 0.05$. For each scenario, 1000 simulations were run. As shown in Table 4, we have >80% power to detect meaningful differences in PROs given the sample size planned for the primary analysis of health service outcomes.

Table 4: Power Calculations for Patient-Reported Outcomes

Total Sample Size (A / B / C)				Difference between arms, in standard deviations	Estimated Power
	Arm A	Arm B	Arm C		
125 / 125 / 125	0	0.10	0.45	0.10, 0.45	85.7%
		0.15	0.45	0.15, 0.45	81.6%
		0.4	0.4	0.4, 0.4	82.8%
		0.25	0.45	0.25, 0.45	82.9%

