Receipt of primary/preventive care, avoidance of non-recommended care, and PROs are secondary endpoints, and the analyses are descriptive. The analysis for receipt of primary/preventive care is similar to that for cancer-related follow-up. The endpoint for the avoidance of non-recommended care will be the proportion of patients who do not receive tests that are not recommended in the year following completion of acute treatment. This will be evaluated as a dichotomous variable (did not receive inappropriate care: yes vs. no). For the patient-reported outcomes, we will report the PRO scores by intervention arm at baseline, 6-month, 12-months, and 18-months. The main PRO analysis will be a comparison of the follow-up scores at 12-months by intervention arm adjusting for baseline. We will also compare the PROs at 6 months for Arms B&C vs. Arm A to evaluate the effective of the in-person transition visit vs. just sending the SCP. For the PLANS, we will report mean (SD) scores at the individual item level. For the ASC, we will primarily report the mean (SD) on the two subscale scores, but will also report the individual items and total score. For the FOCUS Information Needs, we will primarily report total number of health information needs (i.e., number of items endorsed “yes”), but will also report individual needs endorsed (dichotomous). For all of the PROs, we will also explore changes longitudinally using appropriate methods (GEE, random effects) and examine any differences in the trends over time between patient subgroups using interaction tests as needed.

d. Early stopping rules.

Early stopping rules are not applicable to this study.

8. Risks

a. Medical risks, listing all procedures, their major and minor risks and expected frequency.

There is a risk of participants feeling tired, bored, or uncomfortable when answering questions about health and health care.

b. Steps taken to minimize the risks.

Participants do not have to answer any question they do not want to answer.

c. Plan for reporting unanticipated problems or study deviations.

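### The PRO model is described in two ways, and neither names site and cancer type, the factors that stratify randomisation

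*Combined protocol and SAP*

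**What the plan says.** All on PRO analysis is in section 7.c unless noted.

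- DATA ANALYSIS, main analysis: "The main PRO analysis will be a comparison of the follow-up scores at 12-months by intervention arm adjusting for baseline".
- PRO power paragraph before Table 4: "PRO values at follow-up visits will be modeled as a function of study arm while adjusting for the baseline value and other patient characteristics". The further characteristics are not listed there or elsewhere.
- SAMPLE SIZE, on randomisation: "we will stratify by site (JHMI or PRMC) and by cancer type (breast, prostate, or colorectal").
- DATA ANALYSIS, first paragraph: to reflect the stratification, the analysis of follow-up care includes a regression model with cancer type and recruitment site. No such sentence appears for the PROs.
- Schedule (section 4, STUDY IMPLEMENTATION): "Patient-reported outcomes will be collected at baseline, 6, 12, and 18 months".
- Other uses of the visits: "We will also compare the PROs at 6 months for Arms B&C vs. Arm A", and for all PROs "we will also explore changes longitudinally using appropriate methods (GEE, random effects"). Scores are also reported by arm at every visit.
- Status: "PROs are secondary endpoints, and the analyses are descriptive".
- Section 4.f: PRO collection stops at recurrence. Patients may skip surveys; medical records can then supply health service use, but they cannot supply PROs. No handling of missing PRO scores is stated.

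**The concern.** One statement adjusts for baseline. The other is "adjusting for the baseline value and other patient characteristics". An analyst could follow either and reach a different model, and the second leaves the list to be chosen later. Patients and providers know the arm (section 4.c), so a fixed list is better than one chosen after the data are seen.

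Stratified randomisation balances site and cancer type across arms. If these factors predict the PRO and the model omits them, the standard error of the arm contrast is too wide. The plan accepts this reasoning for follow-up care and does not carry it to the PROs.

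There is also a smaller missing-data question. Without a stated method, the default reading of a 12-month comparison is that a patient without a 12-month score drops out of it, even if that patient answered at month 6 or 18. With baseline as the only covariate, this is unbiased if missingness depends only on arm and baseline. A repeated-measures model also allows missingness to depend on the observed 6-month score.

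**Working it through.** **1. The plan's own figure (Table 4).** Inputs: arm means in SD units from Table 4, three-arm ANOVA, alpha 0.05, SD taken as 1. Power comes from the noncentral F distribution with λ = n·Σ(μⱼ − μ̄)²/σ². For means 0, 0.10, 0.45: μ̄ = 0.1833, the sum of squares is 0.1117, and λ = 13.96 at n = 125 or 11.17 at n = 100.

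| Means (A, B, C) | Stated | n = 125 per arm | n = 100 per arm |
|---|---|---|---|
| 0, 0.10, 0.45 | 85.7% | 92.5% | 85.4% |
| 0, 0.15, 0.45 | 81.6% | 90.8% | 83.1% |
| 0, 0.4, 0.4 | 82.8% | 91.3% | 83.7% |
| 0, 0.25, 0.45 | 82.9% | 89.9% | 81.8% |

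Simulation (20,000 runs per row) agrees at n = 125. The stated powers do not reproduce at the labelled 125 per arm; they fit 100 per arm within 2 points. This is a separate labelling matter. It understates power and does not threaten the claim of more than 80%.

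**2. Gain from the strata.** The documents give neither the baseline-to-follow-up correlation ρ nor the share of residual variance R² explained by site and cancer type, so both are assumed. The standard error scales by √(1 − R²):

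- R² = 0.05: √0.95 = 0.975, a fall of 2.5%, equivalent to 1/0.95 = 1.053, or 5% more patients.
- R² = 0.10: √0.90 = 0.949, a fall of about 5%, equivalent to 1/0.90 = 1.111, or 11% more patients.

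For power, take residual variance (1 − ρ²)(1 − R²) with ρ = 0.5 and 100 per arm. Over the four Table 4 scenarios:

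| R² | Power range |
|---|---|
| 0 (baseline only) | 91.7-94.0% |
| 0.02 | 92.2-94.5% |
| 0.05 | 93.0-95.1% |
| 0.10 | 94.3-96.1% |

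The largest gain is 94.3 − 91.7 = 2.6 points.

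**3. Gain from using all visits.** No PRO attrition rate is stated. The 20% in section 7.c belongs to Table 3, the primary outcome. Borrowing it for illustration, 375 × 0.20 = 75 patients would lack a 12-month score. Not all of them could contribute through another visit. Two assumed patterns, each with 20% missing at month 12:

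- Monotone dropout: 10% have no follow-up and 10% have month 6 only, so half of the 75 have another score.
- Intermittent: 5% have none, 5% have month 6 only and 10% have months 6 and 18, so three quarters do.

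With equal correlation ρ of 0.3 to 0.7 between visits, the variance of the 12-month contrast falls by 0.6% to 3.5% (ratios 0.994 to 0.965). Power for A versus C at 0.45 SD rises by at most about 0.4 points (95.7% to 96.1% at ρ = 0.5, intermittent).

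**4. Possible bias.** Assume a true A-versus-C difference of 0.45 SD, month-12 missingness that depends on the 6-month score with about 18-22% missing per arm, and a completers-only model adjusted for baseline (ρ of 0.5 or 0.7). If the dependence is the same in both arms, the estimates are 0.451 and 0.453, so bias is about zero. If it differs by arm, the estimates run from 0.492 to 0.546, a bias of +0.04 to +0.10 SD. The sign follows from the direction assumed. The plan treats 0.5 SD as a meaningful difference.

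**The case against.** The two statements can be read together: the power paragraph gives the general model and DATA ANALYSIS fixes the main time point. On that reading site and cancer type may be among the unnamed characteristics. This is fair, and it limits the point: strata adjustment is unspecified, not excluded. A reader might infer that the plan adjusts for baseline alone, but the power paragraph says otherwise.

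A reader might also infer that the main analysis is restricted to patients with a 12-month score. The plan does not say so; it is only the default reading when no missing-data method is given. Nor are the other visits unused. There is a 6-month comparison, reporting at every visit, and longitudinal models. Choosing one main time point and supporting it with such models is a legitimate design.

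Omitting the strata errs on the conservative side, the PROs are labelled descriptive, and section 2 rests the choice of delivery model on the primary endpoint. All of this stands and keeps the matter minor.

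Finally, one linear mixed model would not suit every PRO. The PLANS knowledge items are single 4-point items and individual FOCUS needs are dichotomous. Because collection stops at recurrence, a likelihood-based model would also implicitly extrapolate scores beyond it. These objections defeat a demand for a mixed model throughout. They do not touch the request to name the covariates.

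**Conclusion.** The point holds in a limited form. The PRO model is specified inconsistently, its further covariates are unnamed, and neither statement includes the stratification factors that the plan uses for follow-up care.

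The size is small: a standard error 2.5-5% lower if the strata explain 5-10% of residual variance, at most about 2.6 power points at ρ = 0.5 and 100 per arm, and at most about 0.4 points from the other visits. Power already exceeds 80% at 100 per arm. Bias arises in the cases examined only when non-response depends on earlier scores differently by arm, which the documents neither show nor rule out. Every one of these figures rests on assumed correlations, R² and missingness patterns.

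The loss of 75 of 375 patients should not be read as the plan's own expectation for the PROs; it borrows the primary outcome's attrition rate. The change is worth making because it is free and closes an open covariate choice. It is a minor improvement, not a defect that threatens the trial's conclusions.

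**What to change.** In section 7.c, state one PRO model and use it in both the power paragraph and DATA ANALYSIS:

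- Adjust the 12-month comparison by arm, and the 6-month comparison of Arms B and C with Arm A, for baseline score, site and cancer type.
- Move any other patient characteristics to a named sensitivity analysis.
- For the scale scores (ASC subscales, FOCUS count of needs), the planned longitudinal model over months 6, 12 and 18, with the same covariates, can supply the 12-month contrast. Patients who miss the 12-month form but answer at another visit then still contribute.
- For single PLANS items and dichotomous FOCUS needs, keep methods suited to the item type, with the same covariates.
- State how missing PRO scores are handled, that scores after recurrence are not collected, and how the model treats them.

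The cost is analysis-plan wording only. Site, cancer type and all visits are already collected, and no patients or contacts are added.
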